## PART 2 Fed via a NG Tube SINCE Randomisation (Please enter 99/99/99 or 99 if unknown)

Date first NG tube inserted after randomisation: day   month   year

Number of tubes inserted SINCE randomisation:

Is the NG tube still in situ? YES  NO

If NO, date last NG tube removed: day   month   year

Name(s) of feed given: \_\_\_\_\_

Did NG tube deliver satisfactory volumes of liquid feed? YES  NO  Uncertain

If NG feeding stopped, please indicate the primary reason below (please tick (✓) one box only)

- Patient taking adequate diet and fluids orally
  - Patient discharged/died
  - Difficulties encountered (please specify difficulties below)
  - Other (e.g. feeding futile), please specify: \_\_\_\_\_
- For office use

Were any difficulties experienced? (please tick (✓) one or more boxes)

- No
  - Difficulties with tube insertion
  - Nasal ulceration
  - Other, please specify: \_\_\_\_\_
  - Patient pulled out the tube(s)
  - Aspiration
- For office use

## PART 3 Fed via another type of tube (e.g. PEG) SINCE Randomisation (Please enter 99/99/99 or 99 if unknown)

Type of tube inserted  Gastric       Duodenal/jejunal

Method of insertion  Endoscopic       Radiological guidance

Date first tube inserted after randomisation: day   month   year

Number of tubes inserted SINCE randomisation:

Is the tube still in situ? YES  NO

If NO, date last tube removed: day   month   year

Name(s) of feed given: \_\_\_\_\_

Did PEG tube deliver satisfactory volumes of liquid feed? YES  NO  Uncertain

If PEG feeding stopped, please indicate the primary reason below (please tick (✓) one box only)

- Patient taking adequate diet and fluids orally
  - Patient discharged/died
  - Difficulties encountered (please specify difficulties below)
  - Other (e.g. feeding futile), please specify: \_\_\_\_\_
- For office use

Were any difficulties experienced? (please tick (✓) one or more boxes)

- No
  - Difficulties with tube insertion
  - Wound infection
  - Haemorrhage from PEG site
  - Other, please specify: \_\_\_\_\_
  - Patient pulled out the tube(s)
  - Aspiration
  - Peritonitis
- For office use

## PART 4 Supplementary Feeds Given SINCE Randomisation (Please enter 99/99/99 or 99 if unknown)

Date supplementary feeding started since randomisation: day   month   year

Number of **missed** doses SINCE randomisation:  (Should receive 3 doses per day)

Are supplementary feeds still being given? YES  NO

If **No**, date last supplementary feed given: day   month   year

Name(s) of feed given: \_\_\_\_\_

If supplementary feeding stopped, please indicate the primary reason below (please tick (✓) **one box only**)

- Patient discharged/died
- Difficulties encountered (please specify difficulties below)
- Other (e.g. feeding no longer appropriate), please specify: \_\_\_\_\_   For office use

Were any difficulties experienced? (please tick (✓) **one or more boxes**)

- No**
- Unable to swallow  Patient refused  Unwanted weight gain
- Any other, please specify: \_\_\_\_\_   For office use

## PART 5 This section should be completed for all patients (Please enter 99/99/99 or 99 if unknown)

SINCE this patient was first randomised have they experienced any of the following: No

- Recurrent stroke If so, first noted since randomisation day   month   year
- Neurological worsening (not clearly due to recurrence) If so, first noted since randomisation day   month   year
- Pneumonia If so, first noted since randomisation day   month   year
- Other infections **1** If so, first noted since randomisation day   month   year
- Please specify: \_\_\_\_\_   For office use

- 2** If so, first noted since randomisation day   month   year
- Please specify: \_\_\_\_\_   For office use

- Pulmonary Embolism If so, first noted since randomisation day   month   year
- Deep vein thrombosis If so, first noted since randomisation day   month   year
- Pressure sores If so, first noted since randomisation day   month   year
- Gastrointestinal haemorrhage If so, first noted since randomisation day   month   year
- Other medical complications **1** If so, first noted since randomisation day   month   year
- Please specify: \_\_\_\_\_   For office use

- 2** If so, first noted since randomisation day   month   year
- Please specify: \_\_\_\_\_   For office use

Did the patient survive to discharge from randomising centre?

YES  NO  If **YES**, go to Part 6

If **NO**, please complete the following

Date of death day   month   year

Primary cause of death (please tick (✓) **one box only**)

- Neurological damage from initial stroke (e.g. coning)  Pneumonia  Pulmonary embolism
- Recurrent stroke  Coronary heart disease
- Other vascular, please specify: \_\_\_\_\_
- Non-vascular, please specify: \_\_\_\_\_

Do you think this patient died due to trial treatment? YES  NO

If **YES**, please specify: \_\_\_\_\_   For office use

Cause of death confirmed by autopsy? YES  NO

## PART 6 FOLLOW-UP DETAILS

Has this patient been discharged to: *(tick (✓) one box only)*

- |  |  |  |
|--|--|--|
|  own home, alone                     |  at home, with partner or relative |  relative's home |
|  residential home                    |  nursing home                      |  other hospital  |
|  other, please specify: _____ |  |  |

If so, **date of discharge** day   month   year

For office use

### Patient details:

**Patient's full postal address on discharge**

(please **PRINT** clearly or attach an address label)

**Post Code**

**Telephone:**

### Family doctor details:

Name of family doctor on discharge

Family doctor's full postal address (please **PRINT** clearly)

**Post Code**

**Telephone:**

*If this patient is NOT registered with a family doctor, please provide the name of a reliable contact below:*

**Contact Name**

**Relationship to patient**

**Full postal address**

(please **PRINT** clearly)

**Post Code**

**Telephone:**

## Part 7 Additional Information

(Please use this space below for any additional information you may think relevant to the trial or to the patient's treatment)

---

---

---

---

---

---

---

---

For office use

**Form completed by:**

**Date:**

**Thank you**

**Now please photocopy this form** (for your own records) **and send the ORIGINAL to the FOOD Trial Co-ordinating Centre, Neurosciences Trials Unit, Western General Hospital, [name]** using the envelopes provided or Fax on [contact]

## The International Stroke Trials Collaboration (Feed Or Ordinary Diet)

### FOLLOW-UP QUESTIONNAIRE

#### CONFIDENTIAL

Dear

On:

you were admitted to:

under the care of:

and, we would like to know how you are now. We need to know what you are **actually managing** to do now, not what you used to do, or would like to do.

Please tick (✓) one box on each line

	YES	NO
Has the stroke left you with any problems?		
Do you need help from anybody with everyday activities?		

**How do you live now?** (please tick (✓) **ONE** box only)

On my own		
With my partner or relatives		

**Where do you live now?** (please tick (✓) **ONE** box only)

In my own home or my relative's home		
In a residential home		
In a nursing home		

In the next section we would like you to read the following descriptions from people who have had similar medical problems to you and choose the one which best describes your present state.

Tick the **ONE** box next to the sentence which best describes your present state.

- I have no symptoms at all
- I have a few symptoms but these do not interfere with my everyday life
- I have symptoms which have caused some changes in my life but I am still able to look after myself
- I have symptoms which have significantly changed my life and I need some help in looking after myself
- I have quite severe symptoms which mean I need to have help from other people but I am not so bad as to need attention day and night
- I have major symptoms which severely handicap me and I need constant attention day and night

We would also like to know how you are **NOW** being fed

- I now consider that I can eat normally
- I am fed via a tube in my nose
- I am fed via a tube in my side

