Even if it were shown that improving nutritional status after stroke would improve outcome, there still remain questions about when to start any supplementary feeding regime and the best way to deliver it. This applies particularly to the important minority of patients who cannot swallow safely. Indeed, increasing emphasis has been placed on detecting those patients with swallowing difficulty so their risk of aspiration pneumonia can be reduced. This is usually done by restricting oral intake and providing fluids, and sometimes food, by alternative routes. Swallowing usually recovers over the first few days or weeks which allows patients to safely take fluids and food, if necessary with a modified consistency (Gordon et al 1987, Barer 1989). However, even during this recovery phase, patients' fluid and food intake may be inadequate and some supplementation by an alternative route may be helpful.

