## ***Six Month Follow-up Form***

---

If the patient is still in hospital when the six month follow-up is due, the randomising clinician will be sent a hospital version of the six month follow-up form which should be completed with the patient (Appendix E).

For those patients who have been discharged, outcome will be assessed blindly via a postal (or telephone if post not possible) questionnaire (Appendix D). This will be sent to the patient directly from the FOOD Trial Co-ordinating Centre or via the National Co-ordinators (for non-UK centres). The questionnaire will establish their:

- Type of residence (own home, with relatives, residential or nursing home)[as a guide to resource use]
- Functional status - degree of functional impairment on the Modified Rankin Scale,
- 'Simple questions', and Health Related Quality of Life (HRQoL) measured using EUROQoL.
- Feeding status - whether they are now feeding normally or still have a feeding tube in place.

Prior to the six month follow-up, their family doctor will be contacted by post or phone to establish the patient's:

- Current address (to allow follow-up).
- Date of death (if applicable).

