**Please tick (✓) ONE box on each line**

	YES	NO
Has the stroke left your patient with any problems?		
Does your patient need help from anybody with everyday activities?		

**Does your patient** (please tick (✓) **ONE** box only)

	YES	NO
Have an NG tube in situ		
Have a PEG tube in situ		

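### The six-month feeding item leaves out some feeding states and asks different questions on the two follow-up forms, so no common feeding status can be formed for all survivors

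*Protocol*

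**What the plan says.** The Protocol section Six Month Follow-up Form treats two groups separately. Patients still in hospital are covered by the hospital version, Appendix E. Of the rest it says "For those patients who have been discharged, outcome will be assessed blindly via a postal" questionnaire, with telephone as the fallback; this is Appendix D. The list of what that questionnaire will establish includes "Feeding status - whether they are now feeding normally or still have a feeding tube in place".

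The feeding item in Appendix D has three options. One is oral, "I now consider that I can eat normally". The other two describe feeding by tube: "I am fed via a tube in my nose" and a matching line for a tube in the side. Unlike the neighbouring items, it does not say whether to tick one box or several.

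Appendix E has two yes/no lines, one for an NG tube and one reading "Have a PEG tube in situ". It has no question on eating, and no other item on either form records feeding.

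The Background section says that swallowing usually recovers early, so that patients can take food and fluids, "if necessary with a modified consistency". The Trial 2 description accepts that some patients will take something by mouth while mainly tube fed.

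**The concern.** There are three linked weaknesses.

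- The stated aim concerns whether a tube is in place, but Appendix D asks whether the patient is fed through one. These differ for a patient who has gone back to oral intake with the tube not yet removed.
- The answers in Appendix D are not exhaustive. Oral but not normal eating, and mixed oral and tube intake, have no clear box.
- Appendix E measures tube presence and Appendix D measures tube use plus normal eating, so the two do not give the same variable.

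The third weakness bears most on any comparison between arms. A patient gets Appendix E because he or she is still in hospital at six months, which is a post-randomisation event. Time to discharge and length of stay are listed secondary outcomes, so the protocol itself allows that allocation may change them. Limiting a feeding comparison to one form would select patients on something that treatment may influence, and pooling the forms would need assumptions that the data cannot test. What a form did not ask cannot be recovered at analysis. The gap matters most in Trials 2 and 3, whose patients enter because they cannot safely take an adequate diet or fluids by mouth.

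**Working it through.** No arithmetic applies, since the protocol gives no figure for feeding status. The check is to take each feeding state a six-month survivor could be in and see what each form would record.

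| State at six months | Appendix D (discharged) | Appendix E (in hospital) |
|---|---|---|
| 1. Eats normally, no tube | First option | No tube; eating not recorded |
| 2. Eats by mouth but not normally, no tube | No clear box | No tube; same as state 1 |
| 3. Eats by mouth, tube present but unused | Tube not recorded | Tube present; use not recorded |
| 4. Partly by mouth, partly by tube | No separate box; may tick a tube option or two options | Tube present; same as state 3 |
| 5. Wholly tube fed | Nose or side option | Tube present; same as state 3 |

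The two halves of the stated status then come out as follows.

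- **Tube in place.** Appendix E records this directly. Appendix D gives it only if every tube in place is assumed to be in use, and it misses state 3.
- **Feeding normally.** Appendix D records this for state 1, with uncertain handling of states 2 to 4. Appendix E does not record it. It could be inferred only by assuming that every inpatient without a tube eats normally, which merges states 1 and 2.

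A status common to all survivors therefore needs at least one of these two assumptions, depending on which half is wanted.

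On size: if a fraction g of discharged survivors eat by mouth but not normally, and a fraction s of those tick the first option, the proportion recorded as eating normally is too high by g × s among respondents to the item. The documents give neither g nor s, so no value can be put on this.

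The last step is to see what else depends on the item. Primary Outcomes uses the Modified Rankin Scale. Secondary Outcomes does not list six-month feeding status; the nearest entry is days of tube feeding. Neither the sample-size paragraphs nor the pre-specified subgroups use it.

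**The case against.** The strongest reply is that little rests on this item. Feeding status at six months is not a listed outcome. The Hospital Discharge Form (Appendix C, Parts 2 and 3) records tube insertion, whether the tube is still in, when it was removed and why feeding stopped, including return to adequate oral intake. That form is also required on eventual discharge for patients still in hospital at six months. This stands, and it is why the point is minor. It does not close the gap: for most patients the form stops at discharge or transfer, the section Duration of Feeding Regimen allows the allocated policy to continue afterwards, and an adequate oral intake is not the same as eating normally.

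Several stronger readings are tempting, and the documents do not support them.

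- *The item cannot measure feeding status at all.* Appendix D does classify normal eaters and tube-fed patients, the two states that the protocol names.
- *Appendix E contradicts the stated aim.* The aim is attached to the questionnaire for discharged patients. The fault is lack of comparability.
- *Every patient on a modified diet lacks a valid answer, and recovery is inflated.* The Trial 1 description counts altered consistency as normal hospital diet, the first option is the patient's own judgement, and the Background remark on consistency concerns early recovery.
- *A patient with mixed intake must choose one box.* The item carries no such restriction. The difficulty is that it does not say.
- *The one-box instruction above the two yes/no lines in Appendix E prevents a double no.* The box layout in the extracted text is unreliable, so nothing is built on this.

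**Conclusion.** The point holds as a minor data-collection defect. The answers in Appendix D are not exhaustive, Appendix D asks about tube use where the protocol promises tube presence, and Appendices D and E cannot be combined into one feeding status without assumptions. The form used depends on a post-randomisation event that allocation may affect.

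Its size cannot be stated. The documents give no proportion of survivors in the uncovered states, none still in hospital at six months, and nothing to show that misclassification would differ between arms. A reader might infer an overstatement of several percentage points in recovery of normal eating, or a threat to the main results. The first would rest on invented inputs. The second is wrong, because the primary analyses and sample sizes do not use the item. What is lost is a comparable description of feeding at six months, chiefly any change after the Hospital Discharge Form is completed.

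**What to change.** Put the same two items on Appendices D and E:

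- (a) current intake: eats normally by mouth; eats by mouth but not normally; fed partly by tube; fed wholly by tube;
- (b) feeding tube in place now: none; nose; side.

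Tell the respondent to tick one box for each item. Item (a) separates the uncovered oral and mixed states, item (b) records presence whether or not the tube is used, and using both on both forms removes the dependence on where the patient is at six months.

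The cost is a reprint of two forms and one or two extra tick boxes per patient. It needs no extra contact and leaves the outcomes and sample sizes as they are.

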**NOW PLEASE TURN OVER** 

FOOD/FU/1/898

# APPENDIX D: Follow-up Form — Reverse

## HEALTH SURVEY

By placing a tick (✓) in ONE box in EACH group below, please indicate which statements best describe your own health state today.

### Mobility

- I have no problems in walking about
- I have some problems in walking about
- I am confined to bed

### Self-Care

- I have no problems with self care
- I have some problems with washing or dressing myself
- I am unable to wash or dress myself

### Usual Activities

- I have no problems with performing my usual activities (eg work, study, housework, family or leisure activities)
- I have some problems performing my usual activities
- I am unable to perform my usual activities

### Pain/discomfort

- I have no pain or discomfort
- I have moderate pain or discomfort
- I have extreme pain or discomfort

### Anxiety/depression

[figure not shown]
- I am not anxious or depressed
- I am moderately anxious or depressed
- I am extremely anxious or depressed

**EXAMPLE**

To help people say how good or bad a health state is, we have drawn a scale (rather like a thermometer) on which the best state you can imagine is marked by '100' and the worst state you can imagine is marked by '0'

Following the example on the right we would like you to indicate on this scale how good or bad your health is today, in your opinion. Please do this by drawing a line from the box 'Your own health today' to whichever point on the scale indicates how good or bad your current state is.

Your own health state today

Did you complete this form yourself (please tick (✓) one box)? Yes

No, it was completed by a relative or friend

Today's date:  day  month  year

**Thank you very much for taking the time to complete this form. Please return it using the pre-paid envelope provided**

## The International Stroke Trials Collaboration (Feed Or Ordinary Diet)

Doctors questionnaire – patient still in hospital at 6 months

### FOLLOW-UP QUESTIONNAIRE

#### CONFIDENTIAL

Dear

**Re:**

**On:**

the above named patient was admitted to:

under your care. It is now time for the six month follow-up of \_\_\_\_\_ and we understand that this patient is still in hospital. We need to know what \_\_\_\_\_ can **actually manage** to do now.

**Please tick (✓) ONE box on each line**

	YES	NO
Has the stroke left your patient with any problems?		
Does your patient need help from anybody with everyday activities?		

**Does your patient** (please tick (✓) **ONE** box only)

	YES	NO
Have an NG tube in situ		
Have a PEG tube in situ		

**Where is the patient NOW?**

Hospital:

Ward:

**Who is responsible for their daily care (if this is NOT you)**

**Please complete this form by asking the following questions.**

In the next section we would like your patient to read the following descriptions and choose the one which best describes their present state. If your patient cannot read or complete the questionnaire, please complete it on their behalf.

**Tick the ONE box next to the sentence which best describes your present state.**

- I have no symptoms at all
- I have a few symptoms but these do not interfere with my everyday life
- I have symptoms which have caused some changes in my life but I am still able to look after myself
- I have symptoms which have significantly changed my life and I need some help in looking after myself
- I have quite severe symptoms which mean I need to have help from other people but I am not so bad as to need attention day and night
- I have major symptoms which severely handicap me and I need constant attention day and night

**NOW PLEASE TURN OVER** 

FOOD/FU6/1/898

# APPENDIX E: Follow-up Form — Hospital Version – Reverse

## HEALTH SURVEY

By placing a tick (✓) in ONE box in EACH group below, please indicate which statements best describe your own health state today.

### Mobility

- I have no problems in walking about
- I have some problems in walking about
- I am confined to bed

### Self-Care

- I have no problems with self care
- I have some problems with washing or dressing myself
- I am unable to wash or dress myself

### Usual Activities

- I have no problems with performing my usual activities (eg work, study, housework, family or leisure activities)
- I have some problems performing my usual activities
- I am unable to perform my usual activities

[figure not shown]
### Pain/discomfort

- I have no pain or discomfort
- I have moderate pain or discomfort
- I have extreme pain or discomfort

### Anxiety/depression

- I am not anxious or depressed
- I am moderately anxious or depressed
- I am extremely anxious or depressed

[figure not shown]
Best imaginable health state  
100

0  
Worst imaginable health state

To help people say how good or bad a health state is, we have drawn a scale (rather like a thermometer) on which the best state you can imagine is marked by '100' and the worst state you can imagine is marked by '0'

### EXAMPLE

Following the example on the right we would like you to indicate on this scale how good or bad your health is today, in your opinion. Please do this by drawing a line from the box 'Your own health today' to whichever point on the scale indicates how good or bad your current state is.

Your own health state today

Are these responses?

The patients  The doctors

Name of person completing the form:

Date:

(Please PRINT clearly)

day  month  year

**Thank you very much for taking the time to complete this form.  
Please return it using the pre-paid envelope provided**

FOOD/FU6/1/898
